#### Intensity

The intensity of an adverse event must be classified using the following 3-point scale:

Mild:	Awareness of signs or symptoms, but no disruption of usual activity.
Moderate:	Event sufficient to affect usual activity (disturbing).
Severe:	Inability to work or perform usual activities (unacceptable).

#### **Causal Relationship to IMP**

The possibility of whether the IMP caused the adverse event must be classified as one of the following:

Reasonable possibility:	There is evidence or argument to suggest a causal relationship between the IMP and the adverse event. The adverse event may occur as part of the pharmacological action of the IMP or may be unpredictable in its occurrence.				
	Examples:				
	• Adverse events that are uncommon but are known to be strongly associated with IMP exposure.				
	• Adverse events that are not commonly associated with IMP exposure, but the event occurs in association with other factors strongly suggesting causation, such as a strong temporal association with the IMP or the event recurs on rechallenge with the IMP.				
No reasonable possibility:	There is no reasonable evidence or argument to suggest a causal relationship between the IMP and the adverse event.				
	Examples:				
	• Known consequences of the underlying disease or condition under investigation.				
	• Adverse events common in the trial population, which are also anticipated to occur with some frequency during the course of the				

trial, regardless of IMP exposure.

## Action Taken to IMP

The action taken to the IMP in response to an adverse event must be classified as one of the following:

- No change (medication schedule maintained or no action taken)
- Discontinued
- Interrupted

## Other Action Taken

Adverse events requiring therapy must be treated with recognized standards of medical care to protect the health and well-being of the subject. Appropriate resuscitation equipment and medicines must be available to ensure the best possible treatment of an emergency situation.

If medication is administered to treat the adverse event, this medication should be entered in the Concomitant Medication Log.

### Date and Time of Outcome

The date and time the subject recovered or died.

### Outcome

The outcome of an adverse event must be classified as one of the following:

- Recovered (fully recovered or the condition has returned to the level observed at initiation of trial treatment)
- Recovered with sequelae (resulted in persistent or significant disability/incapacity)
- Recovering (the event is improving)
- Not recovered
- Fatal

## 8.3 Adverse Events of Special Interest

### 8.3.1 Dizziness / Pre-syncope

Dizziness or symptoms of pre-syncope (e.g. lightheadedness) will be reported as adverse events. Subjects will be instructed that they must lie down immediately if experiencing dizziness or any symptoms of pre-syncope. If symptoms are not resolved, they should contact the site staff as soon as possible for further instructions.

## 8.3.2 Syncope

Syncope is an adverse event of special interest in this trial and any cases of syncope will be reported as adverse events. Syncope is defined as "orthostatic collapse associated with an abrupt, transient, complete loss of consciousness and inability to maintain postural tone, with rapid and spontaneous recovery". In case of syncope, further evaluations including vital signs should be conducted as soon as the event is reported for the assessment of the causal relationship to the IMP.

## 8.3.3 Dysmenorrhea, Abdominal Pain, Pelvic Pain, Lower Back Pain and Dyspareunia

Endometriosis-related pain, i.e. pain located in the abdominal-pelvic area and the lower back area, will be assessed by the subject on the NRS scale on a daily basis. Dyspareunia will also be captured in the e-Diary in case of sexual intercourse. These data will be described as part of the primary and secondary endpoints based on the subjects' recordings in the diary.

Presence of dysmenorrhea, abdominal pain, pelvic pain or lower back pain related to endometriosis as well as menstrual cramp and dyspareunia are not to be reported as an adverse event unless it fulfils the criteria for an SAE.

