#### 6.1.1 **Premature Discontinuation**

In case of premature discontinuation, an end-of-treatment visit (see section 6.4.6) should be arranged as soon as possible (preferably within 7 days of the last ring removal). Subjects who are prematurely discontinued from the treatment due to adverse events will be asked to attend an end-of-trial visit (see section 6.5.1) within 2 weeks of the end-of-treatment visit. If subjects are discontinued for other reasons, the end-of-treatment and end-of-trial visits can coincide.

If a discontinued subject is found with an ongoing adverse event classified as serious or considered to have a reasonable possible causality to the IMP at their last trial visit, the site staff should follow up until the event is resolved (see section 8.6).

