## 8.3.4 Vaginal Bleeding

Vaginal bleeding pattern (no bleeding, spotting, light bleeding, moderate bleeding and heavy bleeding) will be evaluated by the subject in the e-Diary on a daily basis. These data will be described as a secondary endpoint based on the subjects' recordings in the diary. Abnormal vaginal bleeding (e.g. amenorrhea, oligomenorrhea, spotting or menstrual disorder) is not to be reported as an adverse event, unless there are any clinically significant changes from baseline that require medical or procedural intervention (e.g. prescription of tranexamic acid) or it fulfils the criteria for an SAE.

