## 8.3.5 Ring Acceptability

Any feeling of the ring will be assessed by the subject in a ring acceptability questionnaire at the clinic. Discomfort in connection with the ring insertion and/or removal should not be reported as an adverse event unless it requires active management, i.e. discontinuation of IMP. The acceptability of vaginal rings constitutes a secondary endpoint and will be evaluated in detail based on the subjects' answers to the questionnaire. Any occurrence of ring expulsion or ring breaking will also be captured by ring acceptability questionnaire and should not be reported as an adverse event.

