10.2.2 Incidence of Adverse Events

Treatment-emergent adverse events will be summarised

The tables will display the total number of subjects reporting an AE, the percentage of subjects (%) with an AE, and the number of events (E) reported. AEs will be presented by SOC sorted alphabetically and PT sorted in decreasing frequency of occurrence.

Summary tables will be prepared for:

- All treatment emergent adverse events
- Treatment emergent adverse events with an incidence $\geq 5\%$ of subjects in any treatment group
- Treatment emergent related adverse events
- Treatment emergent related serious adverse events
- Treatment emergent non serious adverse events with an incidence ≥ 5% of subjects in any treatment group
- Treatment emergent unrelated adverse events
- Treatment emergent adverse events leading to death
- Treatment emergent adverse events leading to withdrawal
- Treatment emergent mild adverse events
- Treatment emergent moderate adverse events
- Treatment emergent severe adverse events
- Treatment emergent related mild adverse events
- Treatment emergent related moderate adverse events
- Treatment emergent related severe adverse events
- Treatment emergent serious adverse events

Supporting data listings will be provided for:

- All adverse events sorted by centre and subject no.
- All adverse events sorted by MedDRA Preferred Term
- Serious adverse events
- Adverse events leading to death
- Adverse events leading to withdrawal.

The listings will include information whether the AE occurred during the COVID-19 trial hold.

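### Non-serious dyspareunia or worsened endometriosis pain that makes a woman stop the ring is kept out of adverse event recording, so the table and narratives of adverse events leading to withdrawal are incomplete

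*Protocol*

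**What the plan says.** Protocol 8.3.3 sends the disease symptoms to the diary endpoints and takes them out of adverse event recording. Its subject is "Presence of dysmenorrhea, abdominal pain, pelvic pain or lower back pain related to endometriosis as well as menstrual cramp and dyspareunia", and the sentence closes with the rule: "as well as menstrual cramp and dyspareunia are not to be reported as an adverse event unless it fulfils the criteria for an SAE".

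The next two sections use the same device with wider exceptions. For abnormal bleeding, 8.3.4 keeps events out "unless there are any clinically significant changes from baseline that require medical or procedural intervention", or unless serious. For discomfort at ring insertion or removal, 8.3.5 says it "should not be reported as an adverse event unless it requires active management, i.e. discontinuation of IMP".

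On the output side, SAP 10.2.2 plans a table and a listing of "Treatment emergent adverse events leading to withdrawal". SAP 10.2.1 puts the same category in the overview table, and SAP 10.2 promises a written narrative for each such event. SAP 10.2.3.2 gives the 8.3.3 symptoms no adverse event table and points to the efficacy reporting. Protocol 9.8 likewise plans a table of adverse events leading to discontinuation.

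Protocol 6.1.1 asks women who stop because of an adverse event to return for an end-of-trial visit within 2 weeks of the end-of-treatment visit. For everyone else: "If subjects are discontinued for other reasons, the end-of-treatment and end-of-trial visits can coincide".

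**The concern.** Withdrawal because of an adverse event is a main tolerability result for a new device and drug. That table can only contain what was recorded as an adverse event. If the recording rule removes a group of symptoms whatever their consequence, a withdrawal they cause cannot appear there.

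Two situations matter. The first is endometriosis pain that worsens on treatment until the woman stops. The second is painful intercourse with the ring in place: Protocol 5.1.1 recommends against taking the ring out for intercourse, so a contribution from the ring is plausible. In the exclusion the words limiting it to endometriosis come before menstrual cramp and dyspareunia are added, so on plain reading dyspareunia is excluded whatever its cause. A reader comparing withdrawals between arms would not see either situation in the safety tables.

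**Working it through.** No planned figure exists to reproduce, so the check sets the rules side by side.

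1. **Exceptions in the three neighbouring rules**

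| Section | Symptom | Recorded as an adverse event when |
|---|---|---|
| 8.3.3 | endometriosis pain, menstrual cramp, dyspareunia | serious |
| 8.3.4 | abnormal bleeding | serious, or a clinically significant change that needs intervention |
| 8.3.5 | insertion or removal discomfort | it leads to stopping the IMP |

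The 8.3.5 exception does not reach dyspareunia, because it concerns insertion and removal only.

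2. **Could seriousness cover a withdrawal?** Protocol 8.5.1 lists death, threat to life, hospitalization, disability, congenital anomaly and important medical events. Stopping the IMP is not among them. An important medical event is a matter of judgment and would not ordinarily cover non-serious pain.

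3. **Consistency with the general definition.** Protocol 9.8 (footnote) and SAP 10.2 both count a condition present before treatment as treatment-emergent if it becomes more intense after the first ring. For the disease under study, 8.3.3 says the opposite. Nor is the exclusion needed to prevent misattribution: the causality scale in Protocol 8.2.2 already gives known consequences of the underlying disease as an example of no reasonable possibility.

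4. **Following one woman.** She stops in cycle 2 for non-serious dyspareunia without a local finding.
   - Adverse Event Log: no entry for it (8.3.3).
   - Withdrawal table, listing and narrative: absent (SAP 10.2, 10.2.1, 10.2.2).
   - Visits: she stops for another reason, so no separate end-of-trial visit is required (6.1.1). The end-of-trial assessments are still due at her last visit (6.4.6, 6.5.1).
   - Disposition: present by primary reason (SAP 4.4) and in the discontinuation listing (SAP 4.5).
   - End-of-treatment assessments: scheduled, including B&B, PGIS, PGIC, gynecological examination and ring questionnaire (Protocol 6.4.6).
   - Diary: dyspareunia needs no minimum number of scores (SAP 9.1.7.1), so even a shortened cycle contributes. Overall pain needs at least 50% of scores in both parts of a cycle with menses (SAP 9.1.4.1), so the cycle in which treatment ended may have no mean. Earlier evaluable cycles are summarised (SAP 9.3.1).

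5. **Can the diary replace the missing record?** Only in part. Question 4 asks for the worst pain during or after intercourse and does not ask the cause. Question 3 asks about avoidance because of expected endometriosis pain. Neither separates a ring effect from the disease. The ring questionnaire asks about feeling the ring during intercourse (7.2.2.14), but SAP 10.5.4 tabulates it as acceptability.

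6. **Size.** The only related figure is the planning drop-out: 70 × 0.25 = 17.5 per arm. That is drop-out for all reasons, so it is a ceiling under the planning assumption and not an estimate. No document gives the share due to pain or dyspareunia.

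**The case against.** The strongest defence is that this is a deliberate and openly stated choice. The symptoms are the efficacy endpoints, they are scored daily, and stopping because pain is uncontrolled can reasonably be read as lack of efficacy, which the end-of-treatment form captures. Recording them as adverse events too would count the same symptom twice. This argument stands for ordinary fluctuation of disease pain. It does not answer the case where the symptom ends treatment or where the investigator suspects the ring, and the protocol itself made such an exception in 8.3.5.

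Several stronger readings are tempting, and the documents do not support them:

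- *These women vanish from the report.* They do not. Disposition, listings, end-of-treatment assessments and by-cycle summaries still carry them, as set out above.
- *All ring-related pain is barred.* Pelvic pain that the investigator attributes to another cause is outside the exclusion. Clinically significant vaginal irritation or infection is reportable (8.3.6), and so are clinically significant changes on gynecological examination (7.4.12). What stays barred is dyspareunia without such a diagnosis or finding, and endometriosis pain as such. The protocol gives no criteria for deciding which pain is endometriosis-related.
- *These are the most likely withdrawals with this product.* No document says so. The common treatment-related events with the ring in phase 1 were headache, vaginal discharge, nausea and dizziness (Protocol 1.3), although those trials enrolled healthy volunteers.
- *A given percentage per arm would be missing, measured against the 5% cut-off.* Any assumed share would be arbitrary, and the 5% cut-off in SAP 10.2.2 defines two incidence tables, not the withdrawal table.

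**Conclusion.** The point holds as a gap in recording and an internal inconsistency. As written, 8.3.3 leaves the table, listing and narratives of adverse events leading to withdrawal incomplete for non-serious dyspareunia and for worsened endometriosis pain. It also removes the requirement for a separate end-of-trial visit in those women. It contradicts the treatment-emergent definition and is narrower than both neighbouring rules.

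The size cannot be stated. It would need the rate of stopping for these symptoms, which the documents do not give. The planned 70 per arm no longer describes the trial either, since the SAP reports early termination with few subjects and descriptive output only.

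The conclusion rests on two assumptions. One is the plain reading that the limit to endometriosis does not govern dyspareunia. If it does, ring-caused dyspareunia is reportable and only the part about worsened endometriosis-related symptoms remains. The other is that the wording of protocol version 6.0 applied throughout. SAP section 1 says most women were randomized under version 5.0, whose text is not among the documents.

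A reader might infer that the efficacy conclusions are affected. They are not: the point concerns safety reporting only. It is a cheap improvement.

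**What to change.** Reconcile 8.3.3 with 8.3.4, 8.3.5 and the treatment-emergent definition (Protocol 9.8, SAP 10.2) by adding two recording exceptions to 8.3.3:

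1. Any of the listed symptoms is recorded as an adverse event when it is a reason for discontinuing the IMP.
2. Dyspareunia is also recorded when the investigator sees a reasonable possibility that the ring caused it.

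Then compare every reason on the end-of-treatment form with the Adverse Event Log before database lock, and query the mismatches. If the protocol text can no longer be changed, keep the comparison and add a footnote to the withdrawal table stating the 8.3.3 exclusion and the number of women per arm whose recorded reason for stopping was one of these symptoms.

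The cost is a short addition to 8.3.3 and one data check. A few events will appear in both the efficacy and the safety tables, which a footnote can explain. The change concerns recording only and leaves clinical management as it is.

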## 8.3.4 Vaginal Bleeding

Vaginal bleeding pattern (no bleeding, spotting, light bleeding, moderate bleeding and heavy bleeding) will be evaluated by the subject in the e-Diary on a daily basis. These data will be described as a secondary endpoint based on the subjects' recordings in the diary. Abnormal vaginal bleeding (e.g. amenorrhea, oligomenorrhea, spotting or menstrual disorder) is not to be reported as an adverse event, unless there are any clinically significant changes from baseline that require medical or procedural intervention (e.g. prescription of tranexamic acid) or it fulfils the criteria for an SAE.

## 8.3.5 Ring Acceptability

Any feeling of the ring will be assessed by the subject in a ring acceptability questionnaire at the clinic. Discomfort in connection with the ring insertion and/or removal should not be reported as an adverse event unless it requires active management, i.e. discontinuation of IMP. The acceptability of vaginal rings constitutes a secondary endpoint and will be evaluated in detail based on the subjects' answers to the questionnaire. Any occurrence of ring expulsion or ring breaking will also be captured by ring acceptability questionnaire and should not be reported as an adverse event.

## 8.3.6 Vaginal Irritation and/or Vaginal Infection

Upon spontaneous reporting of vaginal irritation and/or vaginal infection including persistent vaginal itching, vaginal dryness, and/or vaginal discharge during the treatment period, an unscheduled gynecological examination can be performed. Vaginal irritation should be graded in accordance with Table 8-1. Clinically significant findings of vaginal irritation and/or vaginal

infection will be reported as an adverse event.

VAGINAL IRRITATION						
PARAMETER	GRADE 1 MILD	GRADE 2 MODERATE	GRADE 3 SEVERE	GRADE 4 POTENTIALLY LIFE- THREATENING		
Vaginal itching	Itching causing no, mild or moderate interference with usual social and functional activities	Itching causing inability to perform usual social and functional activities; may require intervention	NA	NA		
Vaginal edema	Mild-moderate engorgement	Loss of rugae and friability	NA	NA		
Vaginal erythema	Erythema <50% of vaginal surface	Erythema >50% of vaginal surface	NA	NA		
Vaginal dryness	Dryness causing no or minimal interference with sexual function	Dryness causing greater than minimal interference with sexual function or causing frequent discomfort	NA	NA		
Vaginal discharge by patient report	Mild to moderate increase in amount above baseline – no sanitary protection required	Profuse increase in discharge requiring pad or tampon use	NA	NA		
Vaginal discharge as observed by investigator	No pooling	Pooling	NA	NA		

#### Table 8-1 Grading of Vaginal Irritation

Adapted from: Division of AIDS Table for Grading the Severity of Adult and Pediatric Adverse Events, Addendum 1 (Female Genital Grading Table for Use In Microbicide Studies); November 2007.

#### 8.4 **Pregnancy and Pregnancy Outcome**

If a pregnancy occurs, the IMP should be immediately stopped and Ferring Pharmacovigilance must be informed by mail to **second second s** 

### 8.5 Serious Adverse Events (SAEs)

#### 8.5.1 Serious Adverse Event Definition

#### Serious Adverse Events during the Trial

An event is defined a serious adverse event if it:	Guidance
results in death	Any event resulting in a fatal outcome must be fully documented and reported, including deaths occurring within four weeks after the treatment ends and irrespective of the causal relationship to the IMP. The death of a subject enrolled in a trial is per se not an event, but an outcome.
is life-threatening	The term life-threatening refers to an adverse event in which the subject was at immediate risk of death at the time of the event. It does not refer to an event, which may have caused death if it were more severe.
requires in-patient hospitalization or prolongation of existing hospitalization	The term hospitalization means that the subject was admitted to hospital or that existing hospitalization was extended as a result of an event. Hospitalization describes a period of at least 24 hours. Over-night stay for observation, stay at emergency room or treatment on an out-patient basis do not constitute a hospitalization. However, medical judgement must always be exercised and when in doubt the case should be considered serious (i.e. if case fulfils the criterion for a medically important event). Hospitalizations for administrative or social purposes do not constitute an SAE. Hospital admissions and/or surgical operations planned before trial inclusion are not considered adverse events, if the illness or disease existed before the subject was enrolled in the trial, provided that the condition did not deteriorate during the trial.
results in persistent or significant disability/incapacity	Disability/incapacity means a substantial disruption of a person's ability to conduct normal life functions. In doubt, the decision should be left to medical judgement by the investigator.
is a congenital anomaly/birth defect	Congenital anomaly/birth defect observed in any offspring of the subject conceived during treatment with the IMP.
is an important medical event	Medical and scientific judgment should be exercised in deciding whether other situations should be considered serious such as important medical events that might not be immediately life-threatening or result in death or hospitalization but might jeopardize the patient or might require intervention to prevent one of the other outcomes listed in the definition above. Examples of such events are intensive treatment in an emergency room or at home for allergic bronchospasm, blood dyscrasias or convulsions that do not result in hospitalization, or development of drug dependency or drug abuse.

[figure not shown]
# 8.5.2 Collection, Recording and Reporting of Serious Adverse Events SAE Reporting by the Investigator

All SAEs must be reported **immediately** to Ferring Pharmacovigilance as soon as it becomes known to the investigator and not later than within 24 hours of their knowledge of the occurrence of an SAE.

The investigator is responsible for submitting the completed SAE Report Form with the fullest possible details **within 3 calendar days** of his/her knowledge of the SAE.

## SAE Report Form

The SAE Report Form is included in the e-CRF system, and must be completed and submitted according to the instructions provided on the form. In case the e-CRF cannot be accessed and hence the SAE Report Form cannot be filled in within the e-CRF system, a paper SAE Report Form should be used and sent to Ferring Pharmacovigilance using the contact details below.

Completion of the Demographics, Adverse Event Log, Medical History Log and Concomitant Medication Log are mandatory for initial reports and for follow-up reports if any relevant changes have been made since the initial report. Data entries must have been made in the e-CRF for Ferring Pharmacovigilance to access the information.

Additional information relevant to the SAE such as hospital records, results from investigations, e.g. laboratory parameters (that are not already uploaded in the e-CRF), invasive procedures, scans and x-rays, and autopsy results can be faxed or scanned and e-mailed to Ferring Pharmacovigilance using the contact details in the section above. In any case this information must be supplied by the investigator upon request from Ferring. On any copies provided, such details such as subject's name, address, and hospital ID number should be concealed and instead subject number should be provided.

The investigator will supply Ferring and the IRB with any additional requested information such as results of post-mortem examinations and hospital records.

Ferring will report all serious adverse events according to local regulations.

